
Columbia University Irving Medical Center
Herbert Irving Comprehensive Cancer Center
AAAS4165_Version Date: 07/07/2021

| | |
|---------------------------|---|
| | 
if event resolves to Grade 1 or better within 12 weeks;
 
 • Resume Cobimetinib with dose reduced by 1 level if event resolves to Grade 1 or better within 28 days • If event does not resolve, permanently discontinue atezolizumab (if applicable) and cobimetinib and contact PI. |
| Diarrhea colitis, Grade 4 | 
 • Permanently discontinue atezolizumab (if applicable) and cobimetinib and contact PI; • Refer patient to GI specialist (confirmation and biopsy); • Discontinue medications that may exacerbate colitis while investigating etiology; • If Received Atezolizumab – 
 • Initiate treatment with 1-2 mg/kg/day oral prednisone or equivalent. Convert to 1-2 mg/kg/day oral prednisone or equivalent upon improvement; • If event does not improve within 48 hrs after starting corticosteroids, consider immunosuppressive agent; • If event resolves to Grade 1 or better, taper corticosteroids over ≥ 1 month. |

Table A1.3. Guidelines for managing dermatologic events in response to *atezolizumab, cobimetinib, and/or hydroxychloroquine*

| Event | Action |
|------------------|---|
| General guidance | 
 • Seek dermatologic evaluation for persistent and/or severe rash or pruritis • Consider biopsy unless contraindicated |
| Grade 1 or 2 | 
 • Continue atezolizumab (if applicable), cobimetinib, and hydroxychloroquine • Initiate supportive care. If event does not improve, consider treatment with higher potency topical steroids. • For Grade 2, consider referral to dermatologist • For acneiform rash: consider initiating treatment with topical corticosteroids and oral antibiotics, as clinically indicated. |

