| Grade 3 | 
 • Withhold atezolizumab (if applicable), cobimetinib, and hydroxychloroquine; • Refer patient to dermatologist; • If Received Atezolizumab – 
 • If event resolves to Grade 2 or better within 12 weeks, resume atezolizumab at fixed dose. If not, discontinue atezolizumab and cobimetinib and contact PI. • If event resolves to Grade 2 or better within 28 days, resume cobimetinib with dose reduced by 1level. If not, permanently discontinue cobimetinib. • For acneiform rash: consider initiating treatment with topical corticosteroids and oral antibiotics, as clinically indicated. |

Columbia University Irving Medical Center
Herbert Irving Comprehensive Cancer Center
AAAS4165_Version Date: 07/07/2021

| | |
|---------|---|
| | indicated. |
| Grade 4 | 
 Permanently discontinue atezolizumab (if applicable), cobimetinib, and hydroxychloroquine and contact PI. |

Table A1.4. Guidelines for managing hepatic events in response to *atezolizumab, cobimetinib, and/or hydroxychloroquine*

| Event | Action |
|---|---|
| Elevations in ALT, AST, and/or bilirubin | |
| AST/ALT > 3xULN with total bilirubin >ULN to \leq 2xULN | 
 Continue atezolizumab (if applicable), cobimetinib, and hydroxychloroquine, and contact PI. |
| AST/ALT > 3 x ULN to 5 x ULN with total bilirubin > ULN to \leq 2xULN | 
 Continue atezolizumab (if applicable), cobimetinib, and hydroxychloroquine, and contact PI. Monitor LFT weekly; Consider referral to hepatologist and liver biopsy; If Received atezolizumab – 
 For suspected immune-related events lasting >5 days: 
 Consider withholding atezolizumab; Consider initiating 1-2mg/kg/day prednisone or equiv.; If atezolizumab is withheld and event resolves to AST/ALT \leq 2 x ULN within 12 weeks, resume at fixed dose. Otherwise, discontinue atezolizumab and cobimetinib, and contact PI.^{a,b,c} |
| AST/ALT > 5 x ULN to < 10 x ULN with total | 
 Continue atezolizumab (if applicable), |

Columbia University Irving Medical Center
Herbert Irving Comprehensive Cancer Center
AAAS4165_Version Date: 07/07/2021

| | |
|--|---|

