| 
^a Resuming atezolizumab may be considered in patients who are deriving benefit and have fully recovered from the immune-related event. Patients can be re-challenged with atezolizumab only after approval from both the investigator and the PI.
 | |

Table A1.9. Guidelines for managing ocular events in response to *atezolizumab, cobimetinib, and/or hydroxychloroquine*.

| Event | Action |
|--|---|
| General guidance | 
 • Refer patient to ophthalmologist. |
| Serious retinopathy, Grade 1 | 
 • Continue atezolizumab (if applicable), cobimetinib, and hydroxychloroquine; • Refer to ophthalmologist; |
| Serious retinopathy, Grade 2 (tolerable) | 
 • Continue atezolizumab (if applicable) and cobimetinib. • Withhold hydroxychloroquine. • If event resolves to Grade 1, resume hydroxychloroquine at one dose level lower. • Refer to ophthalmologist. |
| Serious retinopathy, Grade 2 (intolerable), Grade 3 or Grade 4 | 
 • Withhold cobimetinib and hydroxychloroquine. • Continue atezolizumab (if applicable). • Complete ophthalmologic examination. • If event improves by at least one grade |

Columbia University Irving Medical Center
Herbert Irving Comprehensive Cancer Center
AAAS4165_Version Date: 07/07/2021

| | |
|--|--|
| | within 28 days, resume cobimetinib and hydroxychloroquine at 1 dose level lower. If not, permanently discontinue cobimetinib and hydroxychloroquine. |
| Retinal vein occlusion | 
 Permanently discontinue cobimetinib and hydroxychloroquine. Continue atezolizumab (if applicable). Treatment as per institutional guidelines. |
| Potential immune-related ocular toxicity, Grade 1 | 
 Continue atezolizumab (if applicable), cobimetinib, and hydroxychloroquine. Complete ophthalmologic examination. Initiate topical corticosteroid eye drops and topical immunosuppressive therapy. If symptoms persist, treat as Grade 2. |

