| Potential immune-related ocular toxicity, Grade 2 | 
 Withhold atezolizumab (if applicable). Continue cobimetinib and hydroxychloroquine. Initiate topical corticosteroid eye drops and topical immunosuppressive therapy. If event resolves to Grade 1 or better within 12 weeks, resume atezolizumab (if applicable). If not, permanently discontinue atezolizumab (if applicable), hydroxychloroquine, and cobimetinib and contact PI.^{a,b,c} |
| Potential immune-related ocular toxicity, Grade 3 or 4 | 
 Permanently discontinue atezolizumab, cobimetinib, and hydroxychloroquine, and contact PI.^c |

^a Corticosteroids must be tapered over ≥ 1 month to ≤ 10 mg/kg/day oral prednisone or

Columbia University Irving Medical Center
Herbert Irving Comprehensive Cancer Center
AAAS4165_Version Date: 07/07/2021

equivalent before atezolizumab may be resumed.

^b Atezolizumab may be withheld for more than 12 weeks to allow for corticosteroid treatment tapering. Course must be agreed upon by the investigator and PI.

^c Resuming atezolizumab may be considered in patients who are deriving benefit and have fully recovered from the immune-related event. Patients can be re-challenged with atezolizumab only after approval from both the investigator and the PI.

Table A1.10. Guidelines for managing cardiac events in response to *atezolizumab, cobimetinib, and/or hydroxychloroquine*.

| Event | Action |
|---|--|
| Asymptomatic LVEF increase from baseline. | |
| LVEF \geq 50% or LVEF 40-49% with <10% absolute decrease from baseline | 
 Continue cobimetinib, atezolizumab (if applicable), and hydroxychloroquine. |
| LVEF < 40% or LVEF 40-49% with \geq 10% absolute decrease from baseline | 
 Withhold cobimetinib and hydroxychloroquine. Continue atezolizumab (if applicable) as clinically indicated. Reevaluate LVEF at 14 days. If patient has <10% absolute decrease from baseline LVEF, resume cobimetinib and hydroxychloroquine with dose level reduced by 1. Reevaluate after 2, 4, 10, and 16 weeks, and then every 12 weeks thereafter, or as clinically indicated. If patient has LVEF <40% or a \geq 10% absolute decrease from baseline, permanently discontinue cobimetinib and hydroxychloroquine. Assess LVEF every 6 weeks, or as clinically indicated, until LVEF recovers to 50% or lower limit of normal. |

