| Symptomatic LVEF decrease from baseline | 
 Withhold cobimetinib and hydroxychloroquine for at least 4 weeks. Consider withholding atezolizumab (if applicable). Refer patient to cardiologist. If atezolizumab is withheld (if applicable), contact the PI to discuss |

Columbia University Irving Medical Center
Herbert Irving Comprehensive Cancer Center
AAAS4165_Version Date: 07/07/2021

| | |
|---------------------------------------|---|
| | 
resuming treatment.
 
 • Reevaluate LVEF at 28 days. • If patient is asymptomatic after treatment break: 
 ◦ Resume cobimetinib and hydroxychloroquine with dose reduced 1 level if <10% absolute decrease from baseline LVEF. ◦ Permanently discontinue cobimetinib and hydroxychloroquine if <40% or ≥10% absolute decrease from baseline. Continue to assess LVEF every 6 weeks. • If patient is symptomatic following treatment break, permanently discontinue cobimetinib and hydroxychloroquine. Assess LVEF every 6 weeks until LVEF recovers to 50% or to the lower limit of normal, or until symptoms resolve. |
| Rhabdomyolysis or CPK elevation | |
| General guidance | 
 • Evaluate for cardiac cause and rhabdomyolysis. • Assess patient for any history of strenuous physical activity, blunt trauma, or recent IM injections. |
| Asymptomatic CPK elevation, Grade 1-3 | 
 • Continue atezolizumab (if applicable) and cobimetinib. • Recheck CPK at least 1/wk |
| Asymptomatic CPK elevation, Grade 4 | 
 • Withhold atezolizumab (if applicable), cobimetinib, and hydroxychloroquine. |

Columbia University Irving Medical Center
Herbert Irving Comprehensive Cancer Center
AAAS4165_Version Date: 07/07/2021

| | |
|---|---|
| | 
• If resolved to Grade 3 or better within 28 days, resume cobimetinib and hydroxychloroquine with dose reduced by one level. If not, permanently discontinue cobimetinib and hydroxychloroquine.^a |
| Rhabdomyolysis or symptomatic CPK elevation | 
• Withhold atezolizumab (if applicable), cobimetinib, and hydroxychloroquine.• If symptoms improve by at least one grade within 28 days, resume cobimetinib and hydroxychloroquine with dose level reduced by one. If not, permanently discontinue cobimetinib and hydroxychloroquine.^a |

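### Table A1.9 lets hydroxychloroquine restart after Grade 3 or 4 retinopathy at a worse grade than it accepts after a tolerable Grade 2 event

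*Combined protocol and SAP*

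**What the plan says.** Table A1.9 (Section 21.1, Appendix 1) has three graded rows for serious retinopathy.

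- **Grade 1:** all study drugs continue, with referral to an ophthalmologist.
- **Grade 2, tolerable:** atezolizumab and cobimetinib continue and hydroxychloroquine is held. The restart rule is "If event resolves to Grade 1, resume hydroxychloroquine at one dose level lower".
- **"Serious retinopathy, Grade 2 (intolerable), Grade 3 or Grade 4":** cobimetinib and hydroxychloroquine are both held, atezolizumab continues, and a complete eye examination is ordered. The restart test is "If event improves by at least one grade", followed by "within 28 days, resume cobimetinib and hydroxychloroquine at 1 dose level lower". If that is not met, both oral drugs stop for good.

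The remaining restart rule in the table, for immune-related ocular toxicity of Grade 2, brings atezolizumab back only at Grade 1 or better within 12 weeks.

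Other sections bear on the same events. Section 3.3.3 reports irreversible retinal damage with hydroxychloroquine in some patients. Section 4.1.1.1 counts certain retinal events in the first 28 days as dose-limiting toxicities (DLTs). Section 8.1 removes a patient with a DLT unless the patient is benefiting. Section 8.2.4 lets a patient continue on two of the three drugs, but on one alone only with Principal Investigator approval. The list of permanent cobimetinib stops in Section 8.3.1 does not mention retinopathy.

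**The concern.** A relative test with no absolute grade lets the end point of recovery depend on how bad the event was. For hydroxychloroquine this reverses the expected order. A patient whose worst grade was a tolerable 2 must return to Grade 1. A patient whose worst grade was 4 may restart at 3. The tolerable Grade 2 row shows that the authors meant to treat hydroxychloroquine more cautiously than cobimetinib, and the severe row drops that distinction without giving a reason.

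At stake is a clear instruction for a serious eye event. Two investigators could follow the table faithfully and act differently: one restarts because the event fell by a grade, and the other keeps holding because the grade reached is one at which the table holds the drug.

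**Working it through.** No sample size, power or error rate is involved, and the plan gives no figure to reproduce. The check treats the table as a decision rule. It follows each starting grade through the smallest improvement that qualifies and compares the result with the table's own action at that grade.

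**Reading 1: rows applied by grade at onset.** The worst grade at which hydroxychloroquine may restart is:

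| Grade at onset | Restart allowed at |
|---|---|
| 2, tolerable | 1 |
| 2, intolerable | 2 − 1 = 1 |
| 3 | 3 − 1 = 2 |
| 4 | 4 − 1 = 3 |

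The threshold goes from 1 to 2 to 3 as the event worsens. Cobimetinib shows no such conflict, because no milder retinopathy row holds it and so there is no stricter threshold to compare with.

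**Reading 2: rows applied by current grade.** The severe row permits restart in four end states. The table's own action at each is:

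| End state | Hydroxychloroquine | Cobimetinib |
|---|---|---|
| Grade 3 (from 4) | held | held |
| Grade 2, intolerable (from 3 or 4) | held | held |
| Grade 2, tolerable (from 3 or 4) | held until Grade 1 | continued |
| Grade 1 or better | continued | continued |

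Hydroxychloroquine may restart in 3 of 4 states where the table holds it, and cobimetinib in 2 of 4. An event that starts at intolerable Grade 2 raises no conflict for either drug, since one grade down is Grade 1.

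**Comparison with other rows.** Several Appendix 1 rows restart cobimetinib at a grade where their own table continues it:

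- Diarrhea or colitis, Grade 2-3 (Table A1.2): "Resume Cobimetinib with dose reduced by 1 level if event resolves to Grade 1 or better within 28 days".
- Dermatologic, Grade 3 (Table A1.3): "If event resolves to Grade 2 or better within 28 days, resume cobimetinib".
- Asymptomatic creatine phosphokinase (CPK) elevation, Grade 4 (Table A1.10): "If resolved to Grade 3 or better within 28 days, resume cobimetinib and hydroxychloroquine with dose reduced by one level".

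Others also lack an absolute grade:

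- In Table A1.8, restart after Grade 4 neuropathy may be considered, and restart after meningoencephalitis is directed, once the patient is stable within 28 days.
- In Table A1.6, cobimetinib resumes after life-threatening hyperthyroidism once the event can be managed clinically.
- Tables A1.10 and A1.13 use an improvement of one grade for rhabdomyolysis or symptomatic CPK elevation, and A1.13 adds that symptoms resolve.

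**Do other rules supply the missing grade?** None does. The DLT rule is limited to an early window in Phase 1 and has a clinical-benefit exception. Referral, the eye examination and 24-hour reporting to the Principal Investigator are actions, not restart conditions. Removal for unacceptable toxicity (Section 5.5.1) applies at any time but names no grade.

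**The case against.** The strongest reply is that the row is already cautious. Both drugs stop permanently unless the event improves within 28 days, so irreversible damage that does not improve never reaches the restart branch. Restart is at a reduced dose, under ophthalmology care and with the Principal Investigator informed. Section 4.1.1 ties hydroxychloroquine eye toxicity to high cumulative doses. If the word serious in these rows is a slip for serous, the term used in the cobimetinib special-interest list in Section 8.3, the link to hydroxychloroquine weakens further. All of this limits the likely harm. It does not remove the inconsistency, because the table holds hydroxychloroquine according to grade, not dose or trend.

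A reader might infer three stronger points that the documents do not support.

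- *That cobimetinib is in conflict outright.* It is so only on the current-grade reading. Section 9.1.1 records events by maximum severity, which sits more easily with the onset reading, although that is a recording rule and not a dosing rule.
- *That this row is the one exception in Appendix 1.* The neuropathy, meningoencephalitis, hyperthyroidism and rhabdomyolysis rows show otherwise.
- *That the first scheduled on-treatment eye examination must fall after any DLT window.* Cycle 3 Day 1 is day 2 × 28 + 1 = 57. Footnote 9 of Table 10 allows 7 days after it, but the column heading allows 3 days either side, so day 54 is possible. That is after the 28-day window but can precede the end of Cycle 2 (day 56), the window named in the synopsis. The severe row orders its own examination in any case.

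**Conclusion.** The point holds for hydroxychloroquine on either reading. After a Grade 3 or 4 event it may restart at Grade 3 or Grade 2, while the milder tolerable Grade 2 event requires Grade 1. For cobimetinib it holds only if the table is applied by current grade, and then only at Grade 3 and intolerable Grade 2. The row is internally inconsistent, not unique.

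The size is that of a wording defect in a safety rule: three of four permitted restart states for hydroxychloroquine, and two or none for cobimetinib. How many patients it could reach is unknown. The conclusion assumes only that the three retinopathy rows describe one kind of event on one grading scale. It does not depend on whether the term is serious or serous. It does not show that patients would be harmed, and it leaves the design, sample size and analyses as they are. It is worth correcting at the next amendment.

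**What to change.** Keep the 28-day limit and the one-level dose reduction. In the row for intolerable Grade 2, Grade 3 or Grade 4, replace the one-grade test with criteria taken from the table's own hold rules:

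- resume hydroxychloroquine only if the event resolves to Grade 1 or better;
- resume cobimetinib only if it resolves to Grade 1 or better, or to tolerable Grade 2;
- otherwise permanently discontinue that drug.

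Leave the existing Principal Investigator and clinical-benefit exceptions, and Section 8.2.4, unchanged. Do not add an override of the Section 8.1 rule that stops all treatment when an oral drug is held for more than 28 days. How that rule fits with drug-specific stops is a separate question, and overriding it here would make the plan less conservative.

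The new wording removes the listed conflicts from the rule itself. It does not guarantee that no patient restarts at a higher grade, because the exceptions remain.

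The cost is one reworded row, with no added visits or tests. Some holds will be longer and a few more patients will stop a drug. At Dose Levels 2 and 3, stopping hydroxychloroquine leaves cobimetinib with atezolizumab, which Section 8.2.4 allows. At Dose Level 1 it leaves cobimetinib alone, so continuing would need Principal Investigator approval. Table 2 assigns an average of 2 to 11 of the 18 patients to that level across its scenarios, and only those with a severe retinal event would be affected.

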8.3.1 Cobimetinib-associated adverse events

For specific guidelines on how to respond to adverse events associated with cobimetinib, see Appendix 1.

The following adverse events are classified as identified risks associated with cobimetinib: serious retinopathy, left ventricular dysfunction, severe hemorrhage, rhabdomyolysis, and pneumonitis. The following adverse events are classified as potential risks for cobimetinib: severe hepatotoxicity (Grade ≥ 3), impaired female fertility, and teratogenicity and developmental toxicity. In addition, there is the possibility of drug-drug interactions in patients treated with cobimetinib. Clinical and safety data were reported that included monotherapy and combination

studies, of which key adverse events are summarized here, but for a complete review of the safety data please refer to the most current IB version.

Common (>10%) adverse events observed with Cobimetinib included bleeding, serious retinopathy, diarrhea, nausea, emesis, rash, pyrexia, chills, anemia, increased liver function enzymes, increased creatinine phosphokinase, and photosensitivity. Less common (1% - 10%) adverse events included decreased left ventricular ejection, risk of basal and squamous cell carcinoma, kertocanthoma, dehydration, hyponatremia, hypophosphatemia, hyperglycemia, and pneumonitis. Guidelines for treatment interruption or discontinuation in the case of adverse events are described in Appendix 1.

Cobimetinib should be permanently discontinued for:

- Grade 4 hemorrhage events attributed to cobimetinib
- Symptomatic or asymptomatic decrease of LVEF < 40% or $\geq 10\%$ absolute decrease from baseline after treatment break or recurrent symptomatic absolute decrease of LVEF < 10% (See Table 1 for details)
- Rhabdomyolysis or symptomatic CPK elevations not improving within 4 weeks of dose interruption
- Liver laboratory abnormalities not resolving to Grade ≤ 1 within 4 weeks of dose interruption or if Grade 4 liver laboratory abnormalities recur after initial improvement
- QTc increase meets values of both > 500 ms and > 60 ms change from pre-treatment values or 3rd occurrence of QTc > 500 ms during treatment and change from pre-treatment value remains ≤ 60 ms

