^a Resuming atezolizumab (if applicable) may be considered in patients who are deriving benefit and have fully recovered from the immune-related event. Patients can be re-challenged with atezolizumab only

Table A1.11. Guidelines for managing hemorrhage and other toxicities in response to *atezolizumab and/or cobimetinib*.

| Event | Action |
|--|--|
| Hemorrhage Note: There are no clinical data on the effectiveness of cobimetinib dose modifications for hemorrhage events | |
| Grade 3 hemorrhage other than cerebral hemorrhage | 
 Withhold cobimetinib. Continue atezolizumab (if applicable). If cobimetinib cannot be resumed within 28 days, permanently discontinue. |
| Grade 4 hemorrhage or any grade cerebral hemorrhage | 
 Permanently discontinue cobimetinib if event is attributed to the drug. Otherwise, withhold cobimetinib. Continue atezolizumab (if applicable). |
| Atezolizumab-related toxicities not described above (if applicable) | |
| Grade 1 | 
 Continue atezolizumab (if applicable) and cobimetinib. |
| Grade 2 (intolerable) | 
 Withhold atezolizumab. Continue cobimetinib. If event resolves to Grade 1 within 12 weeks, resume atezolizumab at fixed |

Columbia University Irving Medical Center
Herbert Irving Comprehensive Cancer Center
AAAS4165_Version Date: 07/07/2021

| | |
|---|--|
| | dose. If not, permanently discontinue atezolizumab. |
| Grade 3 or 4 | 
 Withhold atezolizumab and cobimetinib. If event resolves to Grade 1 within 12 weeks, resume atezolizumab at fixed dose. If not, permanently discontinue atezolizumab. If event resolves to Grade 1 within 28 days, resume cobimetinib at fixed dose. If not, permanently discontinue cobimetinib. |
| Other toxicities not described above | |
| Grade 3 or 4, or intolerable Grade 2 treatment-related toxicities | 
 Withhold atezolizumab and cobimetinib. If event resolves to Grade 1 or better within 12 weeks, resume atezolizumab at fixed dose. If not, permanently discontinue atezolizumab. If event resolves to Grade 1 or better within 28 days, resume cobimetinib with dose level reduced by 1. If not, permanently discontinue cobimetinib. |

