| Asymptomatic CPK elevation, Grade 4 | 
 • Withhold cobimetinib, hydroxychloroquine, and if applicable atezolizumab. • If event resolves to Grade ≤ 3 within 28 days, resume cobimetinib and hydroxychloroquine with dose reduced by one level for cobimetinib. If not, permanently discontinue cobimetinib. • Resumption of atezolizumab may be considered in patients who are deriving benefit after discussion with the Principal Investigator. |
| Rhabdomyolysis or symptomatic CPK elevation | 
 • Withhold all study drugs. • If event improves by at least one grade and symptoms resolve within 28 days, resume cobimetinib and hydroxychloroquine with dose reduced by one level, if possible. If not, permanently discontinue cobimetinib. • Resumption of atezolizumab may be considered in patients who are deriving benefit after discussion with the Principal Investigator. |

Table A1.14. Guidelines for managing Immune-related Myocarditis in response to *atezolizumab, cobimetinib, and/or hydroxychloroquine*.

| Event | Action |
|---------------------------------------|--|
| Myocarditis Events | |
| Grade 1 | 
 • Refer patient to cardiologist. • Initiate treatment as per institutional guidelines. |
| Grade 2 | 
 • Withhold atezolizumab for up to 12 weeks after event onset and contact Principal Investigator • Refer patient to cardiologist. • Initiate treatment as per institutional guidelines and consider antiarrhythmic drugs, temporary pacemaker, ECMO, or VAD as appropriate. • Consider treatment with 1–2 mg/kg/day IV methylprednisolone or equivalent and convert to 1–2 mg/kg/day oral prednisone or equivalent upon improvement, in consultation with Principal Investigator. • If event resolves to Grade 1 or better, resume atezolizumab. • If event does not resolve to Grade 1 or better while withholding atezolizumab, permanently discontinue atezolizumab Principal Investigator. |

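### Tables A1.10 and A1.13 give conflicting, unranked rules for restarting and stopping the oral study drugs after CPK elevation or rhabdomyolysis

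*Combined protocol and SAP*

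**What the plan says.** Appendix 1 has a rhabdomyolysis/CPK block inside the cardiac table (A1.10) and a separate table for the same events (A1.13). Neither refers to the other.

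- **Asymptomatic Grade 4 CPK.** Both tables withhold all drugs first. A1.10: "If resolved to Grade 3 or better within 28 days, resume cobimetinib and hydroxychloroquine with dose reduced by one level". A1.13, on the same recovery trigger: "resume cobimetinib and hydroxychloroquine with dose reduced by one level for cobimetinib".
- **Rhabdomyolysis or symptomatic CPK.** The A1.10 restart condition is "If symptoms improve by at least one grade within 28 days". The A1.13 condition is "If event improves by at least one grade and symptoms resolve within 28 days".
- **Condition not met.** Both A1.10 rows permanently stop cobimetinib and hydroxychloroquine. Both A1.13 rows permanently stop cobimetinib and do not mention hydroxychloroquine.
- **Atezolizumab.** A1.10 footnote a says resumption "may be considered in patients who are deriving benefit and have fully recovered from the immune-related event". A1.13 says "Resumption of atezolizumab may be considered in patients who are deriving benefit after discussion with the Principal Investigator".

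Section 8.3.1 lists, among reasons to stop cobimetinib permanently, "Rhabdomyolysis or symptomatic CPK elevations not improving within 4 weeks of dose interruption". It also says "Guidelines for treatment interruption or discontinuation in the case of adverse events are described in Appendix 1". Section 8.2.4 likewise sends dose changes to Appendix 1 without naming a governing table.

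**The concern.** An investigator facing one of these events finds two current instructions that lead to different doses, different restart decisions and different stopping decisions. The events are not peripheral. Section 8.3.1 classes rhabdomyolysis as an identified cobimetinib risk, Section 8.3 makes rhabdomyolysis or CPK elevation of Grade 3 or higher an event of special interest, and Section 3.3.3 lists proximal myopathy among the hydroxychloroquine risks. Section 17 provides for affiliate sites, so two sites could treat like patients differently while each followed the protocol. What is at stake is patient safety and consistent management.

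**Working it through.** There is no design figure to reproduce. The check sets the rows side by side and applies the dose ladders.

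**Inputs.** The hydroxychloroquine start is 600 mg × 2 = 1200 mg/day (Table 1), with reduction levels of 1000, 800 and 600 mg/day (Table 7). A fourth hydroxychloroquine reduction means stopping (Section 8.2.4). Cobimetinib starts at 40 or 60 mg/day (Table 1), with reduction levels of 40 and 20 mg/day and none lower (Table 6).

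**(a) Asymptomatic Grade 4 CPK, Grade 3 or better within 28 days.** Cobimetinib falls one level under both tables. Hydroxychloroquine on restart:

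| Dose at onset (mg/day) | A1.10 | A1.13 | A1.10 relative to A1.13 |
|---|---|---|---|
| 1200 | 1000 | 1200 | 200/1200 = 16.7% lower |
| 1000 | 800 | 1000 | 200/1000 = 20.0% lower |
| 800 | 600 | 800 | 200/800 = 25.0% lower |
| 600 | stopped | 600 | fourth reduction |

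**(b) Rhabdomyolysis or symptomatic CPK, one grade better, symptoms persisting at day 28.** The A1.10 condition is met and the A1.13 condition is not.

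| Drug and dose at onset (mg/day) | A1.10 | A1.13 |
|---|---|---|
| Cobimetinib 60 | restart at 40 | no restart |
| Cobimetinib 40 | restart at 20 | no restart |
| Cobimetinib 20 | no lower level | no restart |
| Hydroxychloroquine 1200 | restart at 1000 | no restart |
| Hydroxychloroquine 1000 | restart at 800 | no restart |
| Hydroxychloroquine 800 | restart at 600 | no restart |
| Hydroxychloroquine 600 | stopped (fourth reduction) | no restart |

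At cobimetinib 20 mg/day the tables agree on cobimetinib but still differ on hydroxychloroquine, unless that drug is also at its lowest level. With cobimetinib off, Section 8.2.4 allows hydroxychloroquine to continue only with a second study drug or with Principal Investigator approval.

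**(c) Restart condition not met.** A1.10 permanently stops both oral drugs. A1.13 permanently stops cobimetinib and leaves hydroxychloroquine withheld with no stated outcome. Section 8.1 supplies a default: if either oral drug is held for more than 28 days, all treatment stops and the patient leaves the study, unless there is clinical benefit.

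**Number of patients.** This cannot be derived. Section 3.1.4.2 reports Grade 3–4 CPK elevation in 7% on atezolizumab plus cobimetinib. If that rate carried over, 18 × 0.07 ≈ 1.3 Phase 1 patients would have Grade 3–4 elevation. That is not a count of affected patients: it mixes Grade 3 with Grade 4, does not separate symptomatic events, and comes from a two-drug regimen in another trial.

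**The case against.** Several points on the other side have force.

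- **A softer reading of A1.10.** Its one-level reduction does not say that it applies to each drug. But the phrase follows both drug names, and only A1.13 adds a limit to cobimetinib, so the plain readings differ.
- **The if-not clause in A1.13.** In the symptomatic row it follows a qualifier about whether a dose reduction is possible, so it could refer to that. The row above supports reading it as non-recovery. On either reading A1.13 gives no restart while symptoms persist, so conflict (b) remains. The permanent stop of cobimetinib in that row is less certain than the absence of a restart.
- **Existing safeguards.** Section 8.1 has the default stop after 28 days. Section 8.2.2 lets cobimetinib resume after a longer hold if this is approved in discussion with the Principal Investigator. Section 8.3 requires events of special interest to reach the Principal Investigator within 24 hours. Cases can therefore be settled one at a time. This stands and limits the consequences, but none of these provisions says which table to start from.
- **Section 8.3.1 as tie-breaker.** Its criterion is improvement, as in A1.10, so a reader might infer that A1.10 governs. The same section defers to Appendix 1, so it does not settle the matter. Nor does it enforce the stricter A1.13 test.
- **An effect on the trial's results.** A reader might infer that the conflict alters DLT counts or the primary endpoints. The documents do not support this. In (a) cobimetinib is reduced under both tables, so the dose-reduction DLT criterion in Section 4.1.1.1 is triggered alike. Grade 3 or higher creatine kinase with myalgia is a DLT whatever the later restart decision. Section 8.1 also removes patients after a DLT by default, so the conflict matters mainly after the DLT window or under the clinical-benefit exception.

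**Conclusion.** The inconsistency is real and in current text, on three points: the hydroxychloroquine dose after asymptomatic Grade 4 CPK, whether symptoms must resolve before restart after rhabdomyolysis or symptomatic CPK, and whether hydroxychloroquine is permanently stopped on non-recovery. For an affected patient the differences are 16.7% to 25.0% of the daily hydroxychloroquine dose (or stopping versus continuing at 600 mg/day), and restart versus no restart at day 28 for a patient who has improved but still has symptoms. These conclusions rest on the plain reading of both tables and on the ladders in Tables 6 and 7. How often this would arise is unknown. It should be corrected as a matter of patient safety and consistent management. No statistical design figure changes.

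**What to change.** Keep one CPK/rhabdomyolysis rule, in Table A1.13, and delete the block from Table A1.10. Deletion alone would lose instructions found only in A1.10, so the surviving table should:

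1. Require improvement by at least one grade, with symptoms resolved within 28 days, before restart after rhabdomyolysis or symptomatic CPK, unless the sponsor documents another choice. This is proposed as the more protective default; the documents do not show which criterion the sponsor intended.
2. State that both cobimetinib and hydroxychloroquine are permanently discontinued on non-recovery, as A1.10 does now and consistent with the Section 8.1 default.
3. Carry over A1.10 footnote a in its own wording. Its only anchors are in the deleted block, and without it atezolizumab could be resumed on benefit plus discussion alone. The full-recovery condition should stay tied to immune-related events, as the footnote has it.
4. State whether hydroxychloroquine is reduced on resumption after asymptomatic Grade 4 CPK, for the sponsor to confirm.
5. Reword the if-not clause so that it clearly means non-recovery within 28 days.

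Then align the Section 8.3.1 bullet, for example: rhabdomyolysis or symptomatic CPK elevation that has not improved by at least one grade, with symptoms resolved, within 28 days of interruption.

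The cost is a protocol wording change and slightly fewer patients eligible for rechallenge than under A1.10.
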